7.1.3 Handling of Outliers

If outliers are identified, sensitivity analyses eliminating the outlier effects will be performed when relevant and their results compared to those of analyses which include all the data.

7.1.4 Rounding

Data will be presented to the observed number of decimal places. In general, minimums and maximums will be presented to the same level of accuracy as the raw data; means, medians and standard deviation (SD) will be presented to 1 further decimal place. Percentages will be presented to 1 decimal place. P-value (significance level) will be presented with 4 decimal places. P-values below 0.0001 will be presented as <0.0001.

7.1.5 Computation of Derived Data

7.1.5.1 Derivation of Body Mass Index (BMI)

BMI is the ratio between weight (Kilograms) and height² (meters²). The results are rounded to the first decimal.

7.1.5.2 Derivation of Activity Measurement of Effective administered dose (MBq)

Activity measurement of the effective administered dose is derived as the difference between the measured radioactivity of the pre-injection total dose in the syringe (in MBq) and the measured radioactivity of the post-injection residual dose remaining in the syringe (in MBq).

7.1.5.3 Derivation of difference between two dates

For any other event, the duration between 2 dates will be derived using the following formula:

- Duration in Days = (End Date – Start Date) + 1

7.1.5.4 Coding of Variables Using Standard Dictionaries

Medical history, Concomitant medications and adverse events (AE) description will be coded using version 208.10 of the Medical Dictionary for Regulatory Activities (MedDRA). Prior and concomitant medications will be coded using the World Health Organization Drug Dictionary Enhanced (WHO DDE version Q3 2017), and grouped by ATC code level 3.

7.1.5.5 Baseline definition

Baseline is defined as the latest available observation before the study drug administration.

7.2 Protocol Deviations

Protocol deviations are defined as deviations from the procedures outlined in the protocol. Protocol deviations will be provided by the sponsor prior to database lock and summarized in table grouped by major or minor classification.

7.3 Analysis Set Definitions

Taking in account the study design, the particular investigated imaging product administered (two single administrations at V1 and V4) all analyses will be performed on the safety population (Safety Set), which will be comprised of all eligible subjects who have been administered at least one study treatment. The Safety Set (SS) population is equivalent to the intention-to-treat (ITT) population.

Individuals having any major deviations will not be excluded from the SS population.

Subjects participating to the PK/Dosimetry substudy will be included into the PK population which will be used for PK and Dosimetry analysis.

Listings and screening assessments will be generated using the Screened set of subjects that does not exclude the screening failures.

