## **Screening Failures and Drop Outs patients**

For the purpose of this study, an “enrolled patient” is a patient who has signed the informed consent and meets all inclusion and exclusion criteria to participate in the study.

A “screening failure” is a patient who has signed the informed consent, but who does not meet all selection criteria and has not received any study medication as part of this protocol.

For patients not considered eligible after the screening period, the reason for not being eligible must be documented. No additional assessments are needed.

A “drop-out” is a patient who has received the study medication and withdrawn consent during the participation in the trial. A “drop-out” may also be a patient who has been “lost to follow-up” and is presumed to have withdrawn consent prior to the end of the trial procedures. However, in the case where a patient who has signed the informed consent and has received study medication as part of this protocol, but who is (later) found not to meet all selection criteria, this will be considered a “protocol violation”.

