4.3 Enrolment

For the purpose of this study, an “enrolled patient” is a patient who has signed the informed consent and meets all inclusion and exclusion criteria to participate in the study.

Patients with RA will be diagnosed based on ACR/EULAR10 (Classification Criteria for Rheumatoid Arthritis) and will thereafter be evaluated with DAS 28 (Disease Activity Score Calculator for Rheumatoid Arthritis). Patients with AS will be diagnosed based on the ASAS (Classification Criteria for Axial and Peripheral Spondyloarthritis). Each patient will be anonymized and identified with a patient ID number. A unique subject identification number (Patient ID) will be assigned at the start of the Screening Period to each subject who signs the informed consent form until the study termination of the patient. This number will identify the subject throughout the study. Patient IDs will include the 2-digit country code number (SW) and a 3-digit subject number (ex: SW001 for first subject in). In both groups of patients – i.e. RA and AS patients – the introduction of a Bi-DMARD (biological disease-modifying antirheumatic drug) treatment should be indicated at the moment of inclusion in the study. The Bi-DMARD therapy should start on Day 2 of the study. RA patients must have been treated at

least with one DMARD (methotrexate, leflunomide and sulfasalazine) or a combination of them in the last 3 months – before inclusion – and this/these DMARD(s) will be continued in this study. Otherwise, RA patients must have been previously treated with Bi-DMARD before administration of the new Bi-DMARD treatment. The non-response of the previous Bi-DMARD treatment must be documented. AS patients must at least have been treated with NSAID in the last 3 months before inclusion and they should be under the same NSAID treatment during the last 4 weeks before inclusion. For RA patients, anti-tumour necrosis factor (TNF) antibodies, anti-interleukine 6 (IL-6) antibodies and abatacept therapies are to be considered and are authorized in Switzerland as first line Bi-DMARD agents in RA. On the contrary, anti-CD 20 positive lymphocytes antibodies can only be used, if one anti-TNF therapy failed. In the AS patients group, only anti-TNF antibodies can be considered, if NSAID are not sufficient. Ten patients enrolled in the study will be asked to participate in a dosimetry and PK sub-study, irrespective of the group they are part of (RA or AS).

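### SAP 7.3 is internally inconsistent: it restricts the Safety Set to 'eligible' dosed subjects, yet says that major deviators are not excluded

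*SAP*

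**What the plan says.** SAP 7.3 runs all analyses on the Safety Set, apart from the PK and dosimetry work and the listings. It defines that set as "all eligible subjects who have been administered at least one study treatment". It adds "The Safety Set (SS) population is equivalent to the intention-to-treat (ITT) population" and then "Individuals having any major deviations will not be excluded from the SS population".

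SAP 7.2 defines what a deviation is: "Protocol deviations are defined as deviations from the procedures outlined in the protocol".

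Protocol section 4 (Screening Failures and Drop Outs patients) separates two kinds of ineligible patient. A screening failure is someone "who does not meet all selection criteria and has not received any study medication as part of this protocol". For a patient who has consented and been dosed, "but who is (later) found not to meet all selection criteria, this will be considered a" protocol violation.

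Safety is the primary objective (Protocol section 2) and the primary endpoint (SAP 6.1). SAP 7.7 places the safety analyses on the Safety Set, and SAP 7.8.1 divides each adverse event count by the number of subjects in it.

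**The concern.** A safety population is normally defined by exposure alone: whoever received the product is counted. This definition adds a second condition. 'Eligible' is not a neutral word here, because Protocol section 3 (Study Outline) and SAP 4.1 both tie it to the inclusion and exclusion criteria.

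The Protocol anticipates the one patient on whom the two rules can disagree, namely someone injected and afterwards found not to satisfy a criterion. The opening definition in SAP 7.3, taken literally, leaves that patient out. The sentence on major deviations, if it covers eligibility violations, keeps the patient in. Two programmers could build different Safety Sets from the same text, and the choice would then be made with the data in view. What is at stake is the numerator and denominator of the summary tables for the primary objective.

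**Working it through.** **Step 1: set the rules side by side for a patient dosed and later found ineligible.**

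- Protocol section 4: cannot be a screening failure, because that category requires no dosing; is a protocol violation.
- SAP 7.3, definition: dosed but not eligible, so outside the set on a literal reading.
- SAP 7.3, deviations sentence: inside the set, provided the violation counts as a major deviation and the sentence is not limited to subjects already admitted.
- SAP 7.2: deviations are departures from procedures. It does not say that failing a selection criterion is a deviation, or a major one.
- SAP 7.3, equivalence with ITT: does not settle the matter. The SAP gives no separate ITT definition, and under SAP 4.3 an enrolled patient "is a patient who has signed the informed consent and meets all inclusion and exclusion criteria to participate in the study", which brings the eligibility condition back.

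The text does not resolve to a single answer.

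**Step 2: reproduce the plan's own figure.** SAP 4.2 plans 20 patients with Day 56 assessments and expects about 10% not to complete them. 20 / (1 − 0.10) = 22.2, rounded up to 23, which matches the stated figure of approximately 23. The Safety Set definition does not alter it.

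**Step 3: choose a base for the size of the effect.** SAP 4.2 says that at least 80% of the planned sample is evaluable: 0.80 × 20 = 16. Both 16 and 20 count evaluable patients. The Safety Set needs only one injection, so it may be larger, and 23 is the planned recruitment. I therefore use 16, 20 and 23.

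**Step 4: effect of one exclusion (the number one is an assumption).**

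Share of the set:
- 1/23 = 4.3%
- 1/20 = 5.0%
- 1/16 = 6.3%

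If no events occur, the exact two-sided 95% upper limit for the event rate is 1 − 0.025^(1/n):
- n = 23 to 22: 14.8% to 15.4%
- n = 20 to 19: 16.8% to 17.6%
- n = 16 to 15: 20.6% to 21.8%

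If the excluded patient had the only event (exact Clopper-Pearson limits):
- 1/20 = 5.0% (95% CI 0.1% to 24.9%) becomes 0/19
- 1/16 = 6.3% (95% CI 0.2% to 30.2%) becomes 0/15

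With no events, the exclusion barely moves the precision. It matters mainly if the excluded patient is the one with an event.

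**Step 5: check where the patient would still be seen.** SAP 10.3 assigns the listings of adverse events, serious, fatal and drug-related events, laboratory results, ECGs and vital signs to the Screened set. The patient's data appear there on either reading. The summary tables could change, as could the two Section 14 listings assigned to the Safety Set in SAP 10.1 (14.3.2, deaths and serious events; 14.3.4.1, clinically significant laboratory values).

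**The case against.** The best case for the plan is that the SAP as a whole means all treated subjects, and that 'eligible' is only a loose word for patients who passed screening.

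- SAP 4.1 uses 'eligible' for patients who go on to be injected, which does not imply removal in retrospect.
- SAP 7.1.1 describes the total column of the non-PK tables as all patients receiving Annexin, with no eligibility condition.
- SAP 7.4 bases withdrawal percentages on the whole Safety Set, while the shell for Table 14.1.1 bases them on treated subjects. These agree only if the two groups are the same. The shell also lists protocol violation as a reason for withdrawal among treated subjects.
- Table 14.1.2 summarises major deviations within the Safety Set, so major deviators are expected to be in it.
- SAP 7.8 says that all adverse events reported after the first dose will be summarised.

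Most of this stands. It shows that retention is the more natural reading of the SAP taken together. It also defeats a stronger conclusion that a reader might draw from the definition alone: that such a patient would drop out of the primary safety analysis. The documents do not establish that. Nor do they support saying that the patient's safety data would be lost, given the Screened-set listings.

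The objection does not remove the conflict. The eligibility condition is still in the definition, SAP 7.2 does not bring eligibility violations within its deviations, and the supporting passages show intent by implication only.

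**Conclusion.** The point holds as an inconsistency within SAP 7.3. The definition could exclude a dosed patient later found ineligible from the primary safety summaries and adverse event denominators. The deviations sentence, and much of the surrounding text, would keep that patient.

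The size is conditional. The documents report no such patient and give no count. On the assumption of one, the share is about 4% to 6% of the set (1 of 23 to 1 of 16), and a summary rate could fall to zero only on the further assumption that this patient had the sole event. SAP 7.7 plans no formal safety testing, so no test result depends on the denominator. No figure in either document is wrong on this account.

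**What to change.** Delete 'eligible' from the Safety Set definition in SAP 7.3, so that it reads in substance: all subjects who received at least one injection of 99mTc-rhAnnexin V-128, regardless of eligibility or protocol deviations. This agrees with the section's own sentence on major deviations and with the treated-subject denominator in Table 14.1.1.

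It would also help to state in SAP 7.2 that a dosed patient found not to meet the selection criteria is recorded as a deviation and stays in the Safety Set. That would link the SAP to the Protocol's term for this patient.

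The cost is one word, plus an optional sentence. No sample size, table shell or data collection changes. If the tables have already been produced, the clinical study report should state which rule was applied and how many dosed subjects, if any, it left out.

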7.4 Subject Disposition

Frequency distributions will be given for the number of subjects enrolled, treated, withdrawn, and who completed the study assessment periods.

Frequency distributions for the reason of withdrawal will be presented: percentages will be calculated on the basis of the whole safety set. Primary reason for which subjects have been withdrawn from the study at any time will be presented, including the following:

- at their own request or at the request of their legally authorized representative; or
- If, in the Investigator's opinion, continuation in the study would be detrimental to the subject's well-being.

In all cases, the reason for withdrawal must be recorded in the subject's medical records and on the eCRF. If the reason is not known, the reason must be investigated to establish whether the reason was due to an adverse event, and, if so, this must be reported in accordance with the procedures as indicated in the study protocol.

7.5 Description of Demographic and Baseline Characteristics

All variables related to demographics and medical history will be summarized on the safety set.

For medical history, the number and percentage of subjects will be summarized by MedDRA classification preferred term.

Frequency distributions will be given for the number of subjects in the Safety set.

All characteristics will be grouped also by RA/AS subjects' disease.

7.6 Extent of Exposure

Summary statistics of the volume of drug injected in mL as well as the actual dose in MBq and MBq/kg will be summarized in the safety dataset by RA/AS patient disease groups and total and by 1st and 2nd injection.

7.7 Evaluation of Safety

The safety analyses will be performed on the Safety set. All safety analyses will be performed considering the treatment received by the subjects.

Safety will be evaluated by abnormal renal function, hepatic function and coagulation laboratory tests and treatment emergent serious and non-serious adverse event assessments over the study period.

No formal hypothesis testing will be carried out.

No imputations will be used in the analysis of safety data.

7.8 Adverse Events

All AEs reported after the first dose (treatment emergent adverse events, TEAEs) will be summarized and their occurrence rate, will be presented by MedDRA system organ class (SOC) and preferred term (PT), overall and by worst severity level. Within a SOC, PT will be presented in descending order of overall occurrence.

Relationship to the investigational product will be assessed by presenting separately all AEs and AEs at least possibly related to study drug (i.e. cause = study treatment and relationship = probable or possible).

Pre-treatment AE will just be presented in the listings.

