7.8.1 Adverse Event occurrence rate

The occurrence rate of a given AE (i.e. proportion of subjects who experienced an AE) will be calculated by dividing the number of subjects who experienced this AE by the total number of subjects in the Safety set.

When calculating occurrence rates, if a subject has the same AE preferred term reported more than once, then the subject will be reported only once using the worst AE attribute.

Occurrence rate will be presented overall and by worst severity level (i.e. in case a patient experienced several times the same AE, only the worst severity level will be presented in the summary table by severity category).

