7.8.2 Adverse Events Tabulation

Calculated AE duration will be indicated in the listing.

Onset day of an AE will be calculated if both the AE start date and date of dosing are complete and is calculated as:

- Onset day for AE = (AE start date – Date of first dose) + 1 (only if AE start date \geq First dose date)

Duration of an AE will be calculated if both the AE stop and start dates are complete and is calculated as:

- Duration of an AE = (AE stop date – AE start date) + 1

In cases where the start date of an AE is completely known but the AE has not yet resolved at the end of the study, duration of an AE will be calculated as:

- Duration of an unresolved AE = (Study termination date – AE start date) + 1

These observations will be flagged in listings with a greater than sign (i.e. $>$) prior to presentation of the duration.

In case of AE partial dates: if only the day is missing then the first day of the month will be used for start dates and the last day of the month will be used for end dates. In case the AE started on the same month than the first dose and the AE start day is missing, the partial date will be replaced by the first dose date.

If the month is missing no imputation will be done.

If duration of an AE cannot be calculated, the information will be missing from the listing.

Incidence rates, frequencies and summary tabulations will be provided for:

- All TEAEs
- All Treatment Emergent Serious AEs (TESAEs)
- All Treatment Emergent Serious AEs (TESAEs) by severity
- All TEAEs leading to permanent treatment discontinuation
- All TEAEs by severity
- All TESAEs by drug-event relationship
- All TEAEs by drug-event relationship
- All TEAEs leading to death

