**STA01form01v3**

Advanced Accelerator Applications
Protocol: AAA-1001

Table 14.2.4: Summary of Serum concentrations (ng/mL) of rhAnnexin V-128 based on ELISA analysis
Population: PK (N=xx)

Timepoint	Statistic	V-128 (N=xxx)
Before treatment	n	xxx
	Mean (SD)	xx.xx (xx.x)
	Geometric mean (CV)	xx.xx (xx.x)
	Median	xx.x
	Min, Max	xx.x, xx.x
5 minutes	n	xxx
	Mean (SD)	xx.xx (xx.x)
	Geometric mean (CV)	xx.xx (xx.x)
	Median	xx.x
	Min, Max	xx.x, xx.x
10 minutes	n	xxx
	Mean (SD)	xx.xx (xx.x)
	Geometric mean (CV)	xx.xx (xx.x)
	Median	xx.x
	Min, Max	xx.x, xx.x

Data source: listings 16.X.X
Source code: xxxx.ssc. Date/time of run: DDMMYYYY:HH:MM.

Page X of Y

Table 14.2.5: Summary of Volume of distribution (Vz) and systemic clearance (Cl) of rhAnnexin V-128
based on ELISA analysis.

[figure not shown]
Population: PK (N=xx)

Parameter	Statistic	V-128 (N=xxx)
Volume of distribution (Vz)	n	xxx
	Mean (SD)	xx.xx (xx.x)
	Geometric mean (CV)	xx.xx (xx.x)
	Median	xx.x
	Min, Max	xx.x, xx.x
systemic clearance (Cl)	n	xxx
	Mean (SD)	xx.xx (xx.x)
	Geometric mean (CV)	xx.xx (xx.x)
	Median	xx.x
	Min, Max	xx.x, xx.x

Data source: listings 16.x.x

Source code: xxxx.ssc. Date/time of run: DDMMYYYY:HH:MM.

Page X of Y

STA01form01v3

Advanced Accelerator Applications
Protocol: AAA-1002

[figure not shown]
Table 14.2.6 Summary of SEC-HPLC analysis results
Population: PK (N=xx)

Species found	Visit	Statistics	Score
XXXXXX	Day 1	n	XXX
		Total	XXXXXX
		Mean	XXX.X
		SD	XXX.XX
		Median	XXX.X
		Min, Max	XXX, XXX
	24 Hours	n	XXX
		Total	XXXXXX
		Mean	XXX.X
		SD	XXX.XX
		Median	XXX.X
		Min, Max	XXX, XXX

Data source: listing 16.x.x.x

Source code: xxxx.ssc. Date/time of run: DDMMYYYY:HH:MM

Page X of Y

STA01form01v3

Advanced Accelerator Applications

Protocol: AAA-1002

Table 14.3.1.1 Overall Summary of TEAEs
Population: Safety (N=xx)

AE Category	RA (N=xx) n (%) [Events]	AS (N=xx) n (%) [Events]	V-128 Total (N=xx) n (%) [Events]
Treatment emergent AEs	xx (xx.x) [xx]	xx (xx.x) [xx]	xx (xx.x) [xx]
Treatment emergent adverse drug reactions	xx (xx.x) [xx]	xx (xx.x) [xx]	xx (xx.x) [xx]
Treatment emergent SAEs	xx (xx.x) [xx]	xx (xx.x) [xx]	xx (xx.x) [xx]
Treatment emergent serious adverse drug reactions	xx (xx.x) [xx]	xx (xx.x) [xx]	xx (xx.x) [xx]
Treatment emergent AEs leading to withdrawal	xx (xx.x) [xx]	xx (xx.x) [xx]	xx (xx.x) [xx]
Treatment emergent AEs leading to death	xx (xx.x) [xx]	xx (xx.x) [xx]	xx (xx.x) [xx]
...			

Data source: Listing 16.2.x.x.x

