Source code: xxxx.ssc. Date/time of run: DDMMYYYY:HH:MM.

Page X of Y

STA01form01v3

Advanced Accelerator Applications
 Protocol: AAA-1002

Table 14.3.1.2 Occurrence of TEAEs – Number and Percentage of Subjects by System Organ Class and Preferred Term
 Population: Safety

System Organ Class(1)	Preferred Term(1)	RA (N=xx) n (%)	AS (N=xx) n (%)	V-128 Total (N=xx) n (%)
Any adverse event		xx (xx.x)	xx (xx.x)	xx (xx.x)
SOC 1	Any SOC 1	xx (xx.x)	xx (xx.x)	xx (xx.x)
	Term 1	xx (xx.x)	xx (xx.x)	xx (xx.x)
	Term 2	xx (xx.x)	xx (xx.x)	xx (xx.x)
	Term 3	xx (xx.x)	xx (xx.x)	xx (xx.x)
	Term 4	xx (xx.x)	xx (xx.x)	xx (xx.x)
	Term 5	xx (xx.x)	xx (xx.x)	xx (xx.x)
SOC 2	Any SOC 2	xx (xx.x)	xx (xx.x)	xx (xx.x)
	Term 11	xx (xx.x)	xx (xx.x)	xx (xx.x)
	Term 21	xx (xx.x)	xx (xx.x)	xx (xx.x)
	Term 31	xx (xx-x)	xx (xx-x)	xx (xx-x)
	Term 41	xx (xx-x)	xx (xx-x)	xx (xx-x)
	Term 51	xx (xx-x)	xx (xx-x)	xx (xx-x)

[figure not shown]
[1] Coding Dictionary MedDRA, Version XX.X

Note: Occurrences are based on the number of subjects who had one or more event with the same PT within the same SOC

Data source: Listing 16.2.x.x.x

Source code: xxxx.ssc. Date/time of run: DDMMYYYY:HH:MM.

[figure not shown]
Page X of Y

STA01form01v3

Versions:

- 14.3.1.3 Occurrence of Serious TEAEs – Number and percentage of subject by System Organ Class and Preferred Term
- 14.3.1.4 Occurrence of TEAEs leading to permanent treatment discontinuation – Number and percentage of subject by System Organ Class and Preferred Term

STA01form01v3

Advanced Accelerator Applications

Protocol: AAA-1002

Table 14.3.1.5 Occurrence of Serious TEAEs by Severity - Number and Percentage of Subjects by System Organ Class and Preferred Term
 Population: Safety (N=xx)

System Organ Class / Preferred Term [1]	Severity [2]	RA (N=xx) n (%)	AS (N=xx) n (%)	V-128 Total (N=xx) n (%)
All	Mild	xx (xx.x)	xx (xx.x)	xx (xx.x)
	Moderate	xx (xx.x)	xx (xx.x)	xx (xx.x)
	Severe	xx (xx.x)	xx (xx.x)	xx (xx.x)
	Life threatening	xx (xx.x)	xx (xx.x)	xx (xx.x)
	Fatal	xx (xx.x)	xx (xx.x)	xx (xx.x)
System Organ Class 1	Mild	xx (xx.x)	xx (xx.x)	xx (xx.x)
	Moderate	xx (xx.x)	xx (xx.x)	xx (xx.x)
	Severe	xx (xx.x)	xx (xx.x)	xx (xx.x)
	Life threatening	xx (xx.x)	xx (xx.x)	xx (xx.x)
	Fatal	xx (xx.x)	xx (xx.x)	xx (xx.x)
Preferred Term 1	Mild	xx (xx.x)	xx (xx.x)	xx (xx.x)
	Moderate	xx (xx.x)	xx (xx.x)	xx (xx.x)
	Severe	xx (xx.x)	xx (xx.x)	xx (xx.x)
	Life threatening	xx (xx.x)	xx (xx.x)	xx (xx.x)
	Fatal	xx (xx.x)	xx (xx.x)	xx (xx.x)
...				

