System Organ Class 2		xx (xx-x)	xx (xx-x)	xx (xx-x)
...	

Note: Occurrences are based on the number of subjects who had one or more event with the same PT within the same SOC

Data source: Listing 16.2.x.x.x

Source code: xxxx.ssc. Date/time of run: DDMMYYYY:HH:MM.

[figure not shown]
[1] Coding Dictionary MedDRA, Version xx.x

[2] Worst Severity for each AE is considered

Page X of Y

Page 47 of 65

Effective date 01/08/2015

STA01form01v3

Versions:

- 14.3.1.6 Occurrence of TEAEs by Severity - Number and Percentage of Subjects by System Organ Class and Preferred Term

Advanced Accelerator Applications
Protocol: AAA-1002

[figure not shown]
**Table 14.3.1.7 Occurrence of Serious TEAEs by Relationship to study drugs –
Number and Percentage of Subjects by System Organ Class, and Preferred Term
Population: Safety (N=xx)**

System Organ Class [1]	Preferred Term[1]	RA	AS	V-128
		(N=xx)	(N=xx)	(N=xx)
		n (%)	n (%)	n (%)
Any adverse event		xx (xx.x)	xx (xx.x)	xx (xx.x)
DRUG RELATED		xx (xx.x)	xx (xx.x)	xx (xx.x)
SOC 1		xx (xx.x)	xx (xx.x)	xx (xx.x)
	PT 1	xx (xx.x)	xx (xx.x)	xx (xx.x)
	PT 2	xx (xx.x)	xx (xx.x)	xx (xx.x)
NOT DRUG RELATED		xx (xx.x)	xx (xx.x)	xx (xx.x)
SOC 2		xx (xx.x)	xx (xx.x)	xx (xx.x)
	PT 3	xx (xx.x)	xx (xx.x)	xx (xx.x)
	PT 4	xx (xx.x)	xx (xx.x)	xx (xx.x)
SOC 3		xx (xx.x)	xx (xx.x)	xx (xx.x)
	PT 5	xx (xx.x)	xx (xx.x)	xx (xx.x)
SOC 4		xx (xx.x)	xx (xx.x)	xx (xx.x)
	PT 6	xx (xx.x)	xx (xx.x)	xx (xx.x)
	PT 7	xx (xx.x)	xx (xx.x)	xx (xx.x)
	PT 8	xx (xx.x)	xx (xx.x)	xx (xx.x)
SOC 5		xx (xx-x)	xx (xx-x)	xx (xx-x)
	PT 9
	PT 10
	..			

Note: Occurrences are based on the number of subjects who had one or more event with the same PT within the same SOC
Data source: Listing 16.2.x.x.x

Source code: xxxx.ssc. Date/time of run: DDMMYYYY:HH:MM.

[1] Coding Dictionary MedDRA, Version xx.x

STA01form01v3

Versions:

Table 14.3.1.8 Occurrence of TEAEs by Relationship to study drugs – Number and Percentage of Subjects by System Organ Class, and Preferred Term

STA01form01v3

[figure not shown]
Advanced Accelerator Applications
Protocol: AAA-1002

Table 14.3.2 Listing of Deaths and Other Serious Adverse Events
Population: Safety (N=xx)

Cohort: XXX										
Subje	SAE	System Organ Class/ Preferred Term [1]/ Verbatim [1]/	Event date	Event Duration (Days)	Time to Event (Days)	Outcome	Severity	Action(s) taken with study treatment	Relations hip with study treatment	Serious criteria

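### Cheap improvement: exposure is summarised by injection but no TEAE summary table is, so the summary tables cannot show whether non-serious events such as rash or edema appear or recur after the second injection

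*SAP*

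**What the plan says.** **Two injections, each followed by an inquiry.** Patients receive the tracer on Day 1 and again at Day 42 ± 14 days (Protocol section 3). The Synopsis and section 6 have each patient asked about signs of allergy (edema, rash) 24 hours after each injection, at Day 2 and Day 43.

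**Exposure is split.** SAP 7.6 summarises volume and activity "by RA/AS patient disease groups and total and by 1st and 2nd injection", and the shell for Table 14.1.7 has a block for each injection.

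**Adverse events are not split.**
- SAP 7.8 defines one pool: "All AEs reported after the first dose (treatment emergent adverse events, TEAEs) will be summarized".
- SAP 7.8.1 divides "by the total number of subjects in the Safety set", and "if a subject has the same AE preferred term reported more than once, then the subject will be reported only once". The note under the shell for Table 14.3.1.2 repeats this: "Occurrences are based on the number of subjects who had one or more event with the same PT within the same SOC".
- SAP 7.8.2 gives "Onset day for AE = (AE start date – Date of first dose) + 1". There is no counterpart for the second dose.
- The summaries listed in SAP 7.8.2, Tables 14.3.1.1 to 14.3.1.8 and their shells have RA, AS and total columns and no injection column.

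**What partly fills the gap.** Table 14.3.1.1 adds event counts ("RA (N=xx) n (%) [Events"), but by category only, not by preferred term or injection. Table 14.3.2 lists deaths and other SAEs with an event date and a "Time to Event (Days" column. Listings 16.2.7.1 (adverse events) and 16.2.5.1 (study treatment administration) cover the rest.

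**The concern.** Safety and tolerability is the only primary objective. The agent is a recombinant protein given twice, with antibody testing before and after. Whether reactions appear or recur on re-exposure is a basic question for that objective, and the protocol collects data for it after each injection. Laboratory, ECG and vital-sign results are tabulated by visit, so they keep their timing. Adverse events lose theirs when summarised.

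At stake is what a reader of the report's tables can conclude. If rash occurred only at the second injection, or came back in the same patients, the preferred-term table would not show it.

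**Working it through.** **1. The plan's own figure.** SAP 4.2 wants 20 evaluable patients and expects about 10% not to complete Day 56. 20 / (1 − 0.10) = 22.2, rounded up to 23, which matches the stated figure. The point here does not depend on it.

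**2. The counting rule applied to three invented patterns.** Assume 20 patients, all injected twice, rash as the only TEAE, and one event per affected patient per injection. The planned row is the number of patients with at least one rash / 20 = 3/20 = 15.0% each time.

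| Pattern | Row in 14.3.1.2 | Events in 14.3.1.1 | After 1st | After 2nd | Same term after both |
|---|---|---|---|---|---|
| A: same 3 patients, both injections | 3 (15.0%) | 6 | 3/20 | 3/20 | 3 |
| B: 3 patients, 1st only | 3 (15.0%) | 3 | 3/20 | 0/20 | 0 |
| C: 3 patients, 2nd only | 3 (15.0%) | 3 | 0/20 | 3/20 | 0 |

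The preferred-term row cannot tell the three apart. The event count separates A from the others only because rash is assumed to be the only TEAE, and it never separates B from C.

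**3. Onset day.** The second injection may fall from 42 − 14 = Day 28 to 42 + 14 = Day 56. An onset day in that range, counted from the first dose, does not show on which side of the second injection the event fell.

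**4. Denominator.** If 23 patients get the first injection and 20 to 23 the second (an assumption; the actual numbers are not in the documents), 3 patients with an event after the second are 3/23 = 13.0% of the Safety set and at most 3/20 = 15.0% of those re-exposed. The difference is at most 2 percentage points here, so the denominator is the lesser issue.

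**5. Length of the two periods.** From Day 1 to the second injection is 28 − 1 = 27 to 56 − 1 = 55 days. From the second injection to the Day 90 visit (Day 76 to 104) is 76 − 56 = 20 to 104 − 28 = 76 days. A plain before/after split thus compares unequal periods, and a rash weeks later would count like one at 24 hours.

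**6. Partial dates.** SAP 7.8.2 sets a missing start day to the first of the month. With a second injection on the 20th, an event of the 21st recorded without its day would move to the 1st, before the injection. SAP 7.1.2 and 7.7 meanwhile say that safety data are not imputed. No planned AE summary table is split by injection, so the rule moves no event across injections in those tables. In a by-injection table it would.

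**7. What a by-injection table could exclude.** With no event among n patients, the one-sided 95% upper bound is 1 − 0.05^(1/n): 13.9% for n = 20, 17.1% for n = 16 (80% of 20, SAP 4.2), and 31.2% for n = 8 (half of 16 at 1:1).

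**The case against.** The strongest case against is that this is a reporting preference. The study is small, open label and unpowered, with no formal safety testing. Nothing in either document promises AE tables by injection, so no commitment is broken. With about 20 patients, the AE and dosing listings are a workable way to see timing. Table 14.3.2 already dates each SAE, and laboratory, ECG, vital-sign and reactive antibody results are shown by visit. Much of this stands. It limits the point to non-serious TEAEs in the summary tables and keeps it a cheap improvement.

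A second objection is that a plain split would not answer the 24-hour question. It would have no time window, no recurrence count, and no way to see an event that was ongoing at the second injection and then worsened. This is right, and the fix below provides for all three. A third is that every patient starts a biologic on Day 2, so timing cannot be read as cause. That also stands and has to be stated with the table.

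What does not yield is the counting rule. It gives one and the same row for three clinically different patterns, and a few extra rows would separate them.

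**Conclusion.** The point holds as a cheap improvement. For non-serious TEAEs, the planned summary tables cannot show whether events appear or recur after the second injection. In the illustration, three different patterns all read 3 (15.0%). The patterns are invented and assume 20 patients injected twice, but the identity of the rows follows from SAP 7.8.1 whatever the numbers. No sample size, error rate or planned estimate changes.

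A reader might infer three stronger things that the documents do not support:
- That the information is lost. Dated events can be placed from listings 16.2.7.1 and 16.2.5.1, and SAEs are dated in Table 14.3.2.
- That a by-injection table would show what the tracer causes. The biologic started on Day 2 runs through both periods, and the periods differ in length.
- That the imputation wording distorts results by injection in the planned tables. It moves no event between injections there, and SAP 7.8.2 can be read as a specific exception. It becomes relevant only once events are assigned to injections.

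**What to change.** In SAP 7.8, keep the overall tables and add one descriptive TEAE table by SOC and preferred term:
- **Split:** by most recent injection (after the 1st; after the 2nd), with RA, AS and total columns. The denominator is the patients given that injection, and each preferred term counts once per patient per injection.
- **Window:** within each injection, also show events with onset on the injection day or the next day, to match the 24-hour inquiry. State that the full periods differ in length.
- **Recurrence:** a row for patients with the same preferred term after both injections.
- **Assignment:** by onset date. An onset on the date of the second injection counts under the 2nd unless a recorded time shows it came earlier. An event ongoing at the second injection stays under the 1st, but is flagged if a worsening after the second injection is recorded.
- **Partial dates:** events whose recorded date parts fit either injection go in a 'not assignable' row. Do not use the first-of-month rule to assign them. State that SAP 7.8.2 is an exception to the no-imputation statements in SAP 7.1.2 and 7.7.
- **Listing:** add onset day from the most recent injection to the AE listing.
- **Reading:** state that the table describes timing only and cannot separate the tracer from the biologic started on Day 2.

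Cost: one or two extra tables, one listing column and some wording, from dates already planned for collection. The downside is small cells: about 8 to 10 patients per disease group and injection if 16 to 20 patients are split 1:1, which the documents do not report.
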